8.1.2 Assessment of Causality

The relationship to study drug of each adverse event will be assessed using the following definitions:

DEFINITE: Distinct temporal relationship with drug treatment. Known reaction to agent or chemical group, or predicted by known pharmacology. Event cannot be explained by subject's clinical state or other factors.

PROBABLE: Reasonable temporal relationship with drug treatment. Likely to be known reaction to agent or chemical group, or predicted by known pharmacology. Event cannot easily be explained by subject's clinical state or other factors.

POSSIBLE: Reasonable temporal relationship with drug treatment. Event could be explained by subject's clinical state or other factors.

UNLIKELY: Poor temporal relationship with drug treatment. Event easily explained by subject's clinical state or other factors.

UNRELATED: This is an event which occurs before dosing. Event or intercurrent illness is due wholly to factors other than drug treatment.

8.2 Collection and follow up of adverse events

All adverse events, however minor, will be documented in the CRF whether or not the investigator concludes the event to be related to drug treatment.

The adverse event reporting period will be from the time that the subject gives informed consent until the subjects final study visit. In addition, any untoward event that may occur subsequent to the reporting period that the Investigator assesses as possibly, probably or definitely related to the study drug medication should also be reported as an adverse event (AE).

Adverse events may be directly observed, reported spontaneously by the subject or by questioning the subject at each study visit.

All AE should be followed up until they are resolved or the subject's participation in the study ends (i.e. until the final CRF is completed for that subject). In addition, all serious and non-serious adverse events assessed by the Investigator as possibly related to the investigational medication should continue to be followed even after the subject's participation in the study is over. Such events should be followed until resolution, or until no further change can reasonably be expected. Deaths occurring more than 30 days after the final dose, which are considered to be unrelated to the study medication, should not be reported as SAE.

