3.2 Study design

This is a 72-day (excluding screening period and follow up phone call) randomized study with two arms. The study will utilize a crossover design as described below.

Subjects will be randomised to start on dolutegravir 50 mg once daily OR no treatment for the first 28 day dosing phase of the study, then will cross over to the alternative for the second dosing phase, following a 2 week washout period (equivalent to 5+ dolutegravir elimination half-lives). Subjects will be contacted approximately seven days after the final euglycaemic clamp visit for a telephone follow up.

- **Day -28 to 0:** Screening
- **Day 1 (am):** Euglycaemic clamp 1
- **Day 1 (pm) to 28:** Dolutegravir (n=8)/Control (n=8)
- **Day 28 (am):** Euglycaemic clamp 2
- **Day 29 to 43:** Wash out (14 days)
- **Day 44 to 72:** Control (n=8)/Dolutegravir (n=8)
- **Day 72 (am):** Euglycaemic clamp 3
- **Day 100** Post study telephone contact

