3.3 Randomisation

After screening, eligible subjects satisfying the inclusion and exclusion criteria will be randomised 1:1 to one of two arms:

Group 1:

- Dolutegravir 50 mg once daily for the first 28 days of the study.
- No treatment for the last 44 days of the study.

Group 2:

- No treatment for the first 43 days of the study.
- Dolutegravir 50 mg once daily for the last 28 days of the study (day 44-72).

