5.1. Study Treatment Regimen

Group 1

Subjects will receive dolutegravir 50 mg once daily from day 1 for 28 days.

On the evening after the second clamp (day 28) they will cease treatment and will continue study activities for following 44 days.

Group 2

Subjects will receive no treatment from day 1 for 43 days on the day 44 they will initiate dolutegravir 50 mg once daily for 28 days (until day 72).

Dolutegravir will be dispensed by the Chelsea and Westminster NHS Trust pharmacy labelled as clinical trial supply.

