The following study assessments will be performed (subjects must have fasted for at least eight hours):

- Adverse events
- Concomitant medication
- Vital signs (during the clamp procedure vital signs will occur every 30 minutes)
- Height/ weight/ BMI
- Measurement of waist and hip size
- Haematology: complete blood count (FBC) with differential and platelet count (haemoglobin, haematocrit, erythrocyte count, white blood count, differential white blood cell count, platelets)
- Biochemistry safety labs assessment for standard clinical chemistry (fasting glucose, creatinine, sodium, potassium, calcium, aspartate aminotransferase, alanine aminotransferase, bilirubin), including thyroid hormones (TSH, ft4), lipids (triglycerides, cholesterol, cholesterol HDL & LDL Sub-fractions) CRP and Hb1aC
- Urinary analysis (pH, specific gravity, leucocytes, nitrite, protein, glucose, ketones, urobilinogen, bilirubin, erythrocytes) and urine drug screen
- Pregnancy testing and LMP date in WOCBP subjects
- Adiponectin, leptin, ghrelin, testosterone
- Pituitary hormone function tests

- Dietary Questionnaire
- Sleep Questionnaires (PSQI)
- Euglycaemic clamp 1
- Insulin will be titrated 3 times during euglycaemic clamp procedure according to approved and verified formula sheet.
- ECG monitoring at 30 minute intervals during the clamp procedure
- Indirect calorimetry (all participants)

Prior to baseline visit subjects will be randomly assigned to Group 1 or Group 2:

Group 1:

- Dolutegravir 50 mg once daily for the first 28 days of the study.
- No treatment for the last 44 days of the study.

Subject will be dispensed study medication (Dolutegravir 50 mg) and instructed to self-administer the study drugs at home from the morning of day 2 until the morning prior to the next euglycaemic clamp day (Day 27).

Group 2:

- No treatment for the first 43 days of the study.
- Dolutegravir 50 mg once daily for the last 28 days of the study (day 44-72).

Subject will be dispensed study medication (Dolutegravir 50 mg) and instructed to self-administer the study drugs at home from the morning of day 45 until the morning prior to the next euglycaemic clamp day (Day 71).

Day 28

Subjects will be admitted to the unit in the morning and remain on the unit for approximately four to six hours. Group 1 subjects will take their last dose of study medication in the unit in the morning of the visit.

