- Urinary analysis (pH, specific gravity, leucocytes, nitrite, protein, glucose, ketones, urobilinogen, bilirubin, erythrocytes) and urine drug screen
- Pregnancy testing and LMP date in WOCBP subjects
- Adiponectin, leptin, ghrelin, testosterone
- Pituitary hormone function tests
- Dietary Questionnaire
- Sleep Questionnaires (PSQI)

Day 72

Subjects will be admitted to the unit in the morning and remain on the unit for approximately four to six hours. Subjects will take their last dose of study medication (Group 2) in the unit in the morning of the visit.

The following study assessments will be performed (subjects must have fasted for at least 8 hours):

- Adverse events
- Concomitant medication
- Height/ weight/ BMI
- Vital signs (during the clamp procedure vital signs will occur every 30 minutes)
- Measurement of waist and hip size
- Haematology: complete blood count (FBC) with differential and platelet count (haemoglobin, haematocrit, erythrocyte count, white blood count, differential white blood cell count, platelets)
- Biochemistry safety labs assessment for standard clinical chemistry (fasting glucose, creatinine, sodium, potassium, calcium, aspartate aminotransferase, alanine aminotransferase, bilirubin), including thyroid hormones (TSH, ft4), lipids (triglycerides, cholesterol, cholesterol HDL & LDL Sub-fractions) CRP and Hb1aC

- Urinary analysis (pH, specific gravity, leucocytes, nitrite, protein, glucose, ketones, urobilinogen, bilirubin, erythrocytes) and urine drug screen
- Pregnancy testing and LMP date in WOCBP subjects
- Adiponectin, leptin, ghrelin, testosteron
- Pituitary hormone function tests
- Dietary Questionnaire
- Sleep Questionnaires (PSQI)
- Euglycaemic clamp 3
- Insulin will be titrated 3 times during euglycaemic clamp procedure according to approved and verified formula sheet.
- ECG monitoring at 30 minute intervals during the clamp procedure
- Indirect calorimetry (Group 2)

Follow up (Day 100)

The subject will be contacted by telephone approximately 28 days after the final euglycaemic clamp day to check whether they have experienced any adverse events. This follow up phone call should be documented in the subject's notes. WOCBP should take a home pregnancy test.

Early termination visit

If a subject withdraws or is discontinued from the study the subject should attend if at all possible for a discontinuation visit and undergo the following procedures:

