The SAE should be reported immediately to the Principal Investigator (within 24 hours of a member of the study team becoming aware of the event). SAEs, and Suspected Unexpected Serious Adverse Reactions (SUSARS) and pregnancies must be reported to the nominated person at the sponsor research and development office as set by the sponsor standard operating procedures (SOPs) within 24 hours of awareness of the event. All SAEs, SUSARs and pregnancies should also be notified to ViiV Healthcare, regardless of causality or expectedness, per the terms of the contract. The SAE should be reported to ViiV Healthcare within 24 hours of a member of the study team becoming aware of the event. A SAE form should be completed and an assessment of whether the SAE is a Suspected Unexpected Serious Adverse Reaction (SUSAR) conducted by the Principal Investigator.

Section 4.8 in the Summary of Product Characteristics (SmPC) represent the Reference Safety Information to determine expectedness of serious adverse events for expedited reporting.

The Principal Investigator is responsible for determining whether the SAE is a Suspected Unexpected Serious Adverse Reaction (SUSAR) and for reporting this in accordance with Good Clinical Practice (GCP) and applicable regulatory requirements.

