The euglycaemic clamp procedure is associated with a potential risk of hypokalemia. In order to avoid this risk, whole blood potassium will be measured along with electrocardiograph monitoring at 30 min intervals as a safety precaution to detect any tendency toward hypokalemia.

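### The 30-day exemption for unrelated deaths runs from the final dose, so on the planned schedule it covers Days 59 to 72 for Group 1, including clamp 3, and no on-study day for Group 2

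*Combined protocol and SAP*

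**What the plan says.** The last sentence of Section 8.2 sets the rule: "Deaths occurring more than 30 days after the final dose, which are considered to be unrelated to the study medication, should not be reported" as SAEs. The clock starts at the final dose, and the sentence makes no allowance for the crossover.

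In Group 1 dosing ends long before participation does. Section 5.1 says: "On the evening after the second clamp (day 28) they will cease treatment and will continue study activities for following 44 days".

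Three other provisions bear on the same deaths:

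- Section 8.2 runs adverse event reporting from consent to the final study visit, whatever the dosing dates. After that, only events judged possibly, probably or definitely drug-related are to be reported.
- Section 8.3 lists death as a criterion for a serious event, with no limit on time or cause. SAEs go to the principal investigator and the sponsor's research office within 24 hours, and they "should also be notified to ViiV Healthcare, regardless of causality or expectedness".
- Section 3.1 runs the safety endpoint from baseline to Day 100 for all subjects.

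**The concern.** A cut-off tied to the last dose works when dosing and participation end together. Here they do so only for Group 2. For a Group 1 death on, say, Day 65 that is judged unrelated to dolutegravir, Section 8.3 makes it an SAE and Section 8.2 says not to report it as one. Site staff cannot follow both.

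The exempt stretch includes an insulin-clamp day. Appendix 4 says: "The euglycaemic clamp procedure is associated with a potential risk of hypokalemia". Section 8.1.2 grades causality only as a relationship to study drug, and its unrelated category takes in events wholly due to something other than the drug. A death caused by the clamp procedure could therefore properly be classed as unrelated and lose its SAE status in Group 1, while the same death on the same day in Group 2 would keep it. At stake is whether the sponsor learns within 24 hours of a death in an ongoing trial.

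**Working it through.** **Inputs**

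- Cut-off: 30 days after the final dose (Section 8.2).
- Group 1 final dose, Day 28 (Section 6, Day 28 visit): "Group 1 subjects will take their last dose of study medication in the unit in the morning of the visit".
- Group 1 after that (Section 3.3): "No treatment for the last 44 days of the study".
- Group 2 final dose, Day 72 (Section 6, Day 72 visit): "Subjects will take their last dose of study medication (Group 2) in the unit in the morning of the visit".
- Third clamp, both groups (Section 3.2): "Day 72 (am): Euglycaemic clamp 3".
- Follow-up call: about 28 days after clamp 3 (Sections 4.2 and 6).
- Clamp visit window: plus or minus 2 days (Section 6.1).

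**The plan's own calendar.** 28 + 44 = Day 72 and 72 + 28 = Day 100. Both reproduce. The documents give no closing day for death reporting, so it has to be derived.

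**Last day inside the rule = final-dose day + 30**

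| | Group 1 | Group 2 |
|---|---|---|
| Final dose | Day 28 | Day 72 |
| Last day inside the rule | 28 + 30 = Day 58 | 72 + 30 = Day 102 |
| Exempt days up to and including clamp 3 | 72 − 58 = 14 | 0 |
| Exempt days up to Day 100 | 100 − 58 = 42 | 0 |

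**Which Group 1 figure applies.** Section 8.2 ends the reporting period at the final study visit and does not say whether the telephone call is one. If Day 72 is the final visit, 14 days are exempt because of this sentence. If the Day 100 call is, 42 days are.

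**Sensitivity**

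- The dispensing text in Section 6 has home dosing end on Days 27 and 71. If those are taken as the final doses, the last days inside the rule become 57 and 101, and Group 1 has 72 − 57 = 15 exempt days up to clamp 3.
- With the clamp window, Group 1's last covered day ranges from 56 to 60. Clamp 3 falls 10 to 18 days after it, so it is never covered.
- Group 2's limit moves with clamp 3 (Day 100 to Day 104). It always falls 30 − 28 = 2 days after that group's own call.

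**The case against.** The best defence is context. The sentences just before the rule concern follow-up after participation has ended, so the rule may have been meant as a post-study limit. But it carries no such limit, and Section 8.2 already confines reporting after the period to drug-related events. An unrelated death after the final visit is excluded without this sentence. On the planned schedule the sentence changes the outcome only inside Group 1's reporting period.

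Several stronger inferences are tempting, and the objections to them stand:

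- **That a death would go unrecorded.** It would not. Section 8.2 has every adverse event documented in the CRF whether or not it is related, so the death would still appear as an adverse event.
- **That 42 exempt days against none is the settled size.** It depends on the Day 100 call being the final study visit. If Day 72 is, unrelated deaths after it fall outside routine reporting in both groups. For the same reason, Day 102 is only the reach of the 30-day rule, and Group 2's working window may be shorter.
- **That notification regardless of causality contradicts the exemption.** That clause governs events already classed as SAEs and does not decide which deaths are. The conflict is with the definition in Section 8.3.
- **That every clamp death is exempt.** Section 8.1.2 separates unlikely from unrelated, and only the latter is literally exempt. A life-threatening clamp event that is not fatal remains an SAE.
- **That never-dosed Group 2 subjects fall into a gap.** With no final dose the exemption cannot be triggered, so the general rule applies to them.

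**Conclusion.** The point holds as a minor safety-reporting correction. On the nominal schedule, with in-unit final doses on Days 28 and 72, Section 8.2 removes SAE status from unrelated deaths on 14 on-study days in Group 1, including the clamp 3 day, and on none in Group 2. The number becomes 42 if the Day 100 call is the final study visit. The text conflicts with Section 8.3 on either reading.

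A reader might go further and infer a biased safety comparison between dolutegravir and no treatment. The documents do not support that. Deaths are still captured as adverse events, the safety analysis is descriptive, and in 16 healthy volunteers the expected number of deaths is near zero. The primary endpoint is not touched. The loss is prompt notification, in one sequence only.

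**What to change.** Reconcile Section 8.2 with Section 8.3 so that the exemption cannot apply while a subject is still on study. A possible wording: *All deaths from consent to the Day 100 contact, or to 30 days after the last dose if later, are reported as SAEs regardless of causality, in both groups.*

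Two clarifications belong with it:

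- State whether the Day 100 call is the final study visit. The call date also needs reconciling, since the text of Section 3.2 puts it about seven days after the final clamp (72 + 7 = Day 79), while its own schedule and Sections 4.2 and 6 give Day 100 or 28 days.
- If relatedness to a study procedure is to decide what is reported after that point, add it to Section 8.1.2, which now covers the drug only.

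The cost is one replaced sentence and one clarification, plus an addition to the causality definitions if the last option is taken. No new visits are needed.

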8.3 Serious Adverse Events (SAE)

A serious adverse event is any untoward medical occurrence that at any dose:

- i) Results in death
- ii) Is life threatening
- iii) Requires in patient hospitalisation or prolongation of existing hospitalisation
- iv) Results in persistent or significant disability/ incapacity
- v) Is a congenital anomaly/ birth defect.
- vi) Medical or scientific judgment should be exercised in deciding whether reporting is appropriate in other situations, such as important medical events that may not be immediately life-threatening or result in death or hospitalisation but may

jeopardise the subject or may require medical or surgical intervention to prevent one of the other outcomes listed in the above definition. These should also be considered serious. Examples of such events are invasive or malignant cancers, intensive treatment in an emergency room or at home for allergic bronchospasm, blood dyscrasias or convulsions that do not result in hospitalisation, or development of drug dependency or drug abuse.

vii) All events of possible drug-induced liver injury with hyperbilirubinemia defined as ALT $\geq 3 \times \text{ULN}$ and bilirubin $\geq 2 \times \text{ULN}$ ($>35\%$ direct).

NOTE: bilirubin fractionation is performed if testing is available. If unavailable, the presence of detectable urinary bilirubin on a dipstick (indicating direct bilirubin elevations and suggesting liver injury) should be recorded. If testing is unavailable and a subject meets the criterion of total bilirubin $\geq 2 \times \text{ULN}$, then the event is still reported as a serious adverse event. If INR is obtained, include values on the serious adverse event form. INR elevations >1.5 suggest severe liver injury.

The SAE should be reported immediately to the Principal Investigator (within 24 hours of a member of the study team becoming aware of the event). SAEs, and Suspected Unexpected Serious Adverse Reactions (SUSARS) and pregnancies must be reported to the nominated person at the sponsor research and development office as set by the sponsor standard operating procedures (SOPs) within 24 hours of awareness of the event. All SAEs, SUSARs and pregnancies should also be notified to ViiV Healthcare, regardless of causality or expectedness, per the terms of the contract. The SAE should be reported to ViiV Healthcare within 24 hours of a member of the study team becoming aware of the event. A SAE form should be completed and an assessment of whether the SAE is a Suspected Unexpected Serious Adverse Reaction (SUSAR) conducted by the Principal Investigator.

Section 4.8 in the Summary of Product Characteristics (SmPC) represent the Reference Safety Information to determine expectedness of serious adverse events for expedited reporting.

The Principal Investigator is responsible for determining whether the SAE is a Suspected Unexpected Serious Adverse Reaction (SUSAR) and for reporting this in accordance with Good Clinical Practice (GCP) and applicable regulatory requirements.

8.4 Liver Events and possible suicide related events

Additional reporting for Liver Events and Possible Suicide Related Events are detailed in Appendix 5 and Section 7.5, respectfully.

9 Data handling

The results from the data collected during the study will be recorded in the Subjects Case Report Form (CRF). In order to maintain confidentiality, the subject will be identified only by subject number and initials.

9.1 Recording of Data

All data collected during the study will be recorded in an individual, subject specific CRF. All CRF should be completed legibly in black ink by an appropriate member of the study team who should be identified and agreed by the Principal Investigator before the start of the study. A delegation of responsibility signature log identifying personnel who can enter data and/or sign off a CRF will be maintained by the Principal Investigator.

Corrections to the data on the CRF will only be made by drawing a single line through the incorrect data (so as not to obscure the original entry) and inserting the correct data next to the original entry. The incorrect data must never be obliterated using correction fluid (e.g. Snopake® or Tippex®). Each correction will be initialised and dated by the person making the correction.

CRF should be kept current to enable the study monitor to review the subject status throughout the course of the study. CRF will be completed, reviewed and signed off by the Investigator within two weeks of the last subject visit.

9.2 Source Documentation and Study Records

The subject's number and date of entry into the study, along with a study identifier, should be recorded in the subject's study records. The following should also be recorded in the study records; confirmation of written and oral consent, the subject's clinical status, date of every study visit, date study medication was started and stopped, concomitant medications, copies of all relevant reports and laboratory tests, comments on results and reference to any adverse events.

Euglycaemic clamp data will not be entered into the subject notes and the formula spreadsheet for this procedure will be considered to be source.

9.3 Data Management

Data will be entered into a study specific database by designated staff on a regular basis from completed Case Record Forms (CRF). Data will be entered on a regular basis to ensure it is up to date. The database will be kept by SMART-TRIAL. Access to the database will be given to authorised personnel only and a log of authorised personnel will be stored in the trial master file.

